4.4.2.2.2 Intensity

Intensity for unsolicited AE will be derived according to the following classification:

Grade 0 (None), Grade 1, Grade 2, Grade 3, or Unknown (or missing).

If the unsolicited AE is measurable and its preferred term is part of the list of solicited reactions, then the measurement is derived based upon and following the same rule than the intensity scales defined in the protocol for that measurable injection site or systemic reaction.

Intensity for the other unsolicited AEs will correspond to the value reported in the CRF.

The maximum intensity corresponds to the highest intensity for a unique term.

4.4.2.2.3 Last Vaccination

Last vaccination before an unsolicited AE is derived from the start date of the unsolicited AE provided in the CRF and is calculated as follows:

- If an unsolicited AE has a complete start date and different to any of the vaccination dates, the start date is used to determine the last vaccination before the unsolicited AE
- If the start date is missing or partially missing, or equal to any vaccination date, then the visit number in the “Appeared after Visit” or similar field, is used to determine the last vaccination before the unsolicited AE.

4.4.2.2.4 Time of Onset

Time of onset is derived from the start date of the unsolicited AE and the date of last vaccination as described in [Section 4.4.2.2.3](#):

Time of Onset = start date of the unsolicited AE - date of last vaccination before the unsolicited AE (if D0 is the first vaccination day).

The time of onset is considered as missing only if one or both dates are missing or partially missing.

The unsolicited AEs will be analyzed “Within 30 days” after each vaccination, which corresponds to AEs with a time of onset between day 0 and day 30.

Unsolicited AE that occurred before vaccination (negative time of onset) will not be included in analysis but will be listed separately.

Unsolicited AE which is non-serious, non-AESI and non-MAAE that occurred with a time of onset higher than defined above will not be included in analysis but will be listed separately.

- For unsolicited AE with missing day, month and year, the unsolicited AE will be classified as “Within 30 days”
- For unsolicited AE with partially missing start date, the partial available information will be used to determine if this AE is classified “Within 30 days” or “Not within 30 days”. An AE will be categorized as “Not within 30 days” only if there is clear evidence from the

partially missing start date that this AE happens before the first vaccination or after the last vaccination + 30 days. In all other situations, this AE is considered as “Within 30 days”. Situations may happen as:

- If the start date of AE has missing Day and non-missing Month and Year
 - If the “Month/Year of AE start date” < “Month/Year of first vaccination date”, then it is clear that this unsolicited AE happened before the first vaccination and this unsolicited AE will not be included in the analysis but will be listed separately.
 - Else if the “Month/Year of last vaccination date” <= “Month/Year of AE start date” <= “Month/Year of (last vaccination date + 30 days)”, then this unsolicited AE will be categorized as “Within 30 days”.
 - Else if the “Month/Year of AE start date” > “Month/Year of (last vaccination date + 30 days)”, then this unsolicited AE will be categorized as “not within 30 days”. If the AE is non-serious, non-AESI and non-MAAE, then it will not be included in the analysis but will be listed separately.
- If the start date of AE has missing Day and Month and non-missing Year:
 - If the “Year of AE start date” < “Year of first vaccination date”, then it is clear that this unsolicited AE happens before the first vaccination and this unsolicited AE will not be included in the analysis but will be listed separately.
 - Else if the “Year of last vaccination date” <= “Year of AE start date” <= “Year of (last vaccination date + 30 days)”, then this unsolicited AE will be categorized as “Within 30 days”.
 - Else if the “Year of AE start date” > “Year of (last vaccination date + 30 days)”, then this unsolicited AE will be categorized as “not within 30 days”. If the AE is non-serious, non-AESI and non-MAAE, then it will not be included in the analysis but will be listed separately.

A few examples of missing time of onset with start date of AE partially missing:

First injection date	Last injection date	Start date of the AE	Injection date + 30	Will be analyzed “Within 30 days” ?
16Oct2023	16Oct2023	Missing	N/A	Y
16Oct2023	16Oct2023	Sep2023	N/A	N
16Oct2023	16Oct2023	Oct2023	15Nov2023	Y
16Oct2023	16Oct2023	Nov2023	15Nov2023	Y
16Oct2023	16Oct2023	Dec2023	15Nov2023	N
05Jan2023	05Jan2023	2022	N/A	N

First injection date	Last injection date	Start date of the AE	Injection date + 30	Will be analyzed “Within 30 days” ?
16Oct2023	16Oct2023	2023	15Nov2023	Y
08Dec2023	08Dec2023	2024	07Jan2024	Y
16Oct2023	16Oct2023	2024	15Nov2023	N

Time of onset period is displayed as D0-D3, D4-D7, D8-D14, D15 or later, and Missing.

Note: For project at a later stage, even if it's recommended to use the above rule, it's possible to follow the below rule, for homogeneity need:

The unsolicited AEs will be analyzed “Within 30 days” after each vaccination, which corresponds to Aes with a time of onset between day 0 and day 30 or missing .An AE with missing time of onset will be considered to have occurred just after the last vaccination (computed according to the [section 4.4.2.2.3](#)), so will be included in these tables.

4.4.2.2.5 Duration

Duration is derived from the start and stop dates of the unsolicited AE :

Stop date of unsolicited AE - start date of unsolicited AE + 1.

The duration should be considered as missing only if one or both of the start and stop dates of the unsolicited non-serious AE is missing or partially missing.

4.4.2.3 SAEs (including AESIs)

An event will be considered as a serious event if “Yes” is checked for “Serious” in the CRF.

An event will be considered as a AESI if “Yes” is checked for “Is the event an AESI?” in the CRF.

SAEs and AESI will be analyzed throughout the study using the following periods:

- Within 7 days after vaccination
- Within 30 days after vaccination
- During the study (i.e., all SAEs/AESI occurred during the study)

4.4.2.4 Medically-Attended Adverse Event (MAAE)

An event will be considered as an MAAE if “Yes” is checked for “Is the event an MAAE?” in the CRF.

MAAEs will be analyzed throughout the study using the following periods:

- During the entire study period after any dose from D0 to last phone call (i.e., all MAAEs that occurred during the study)
- From Day 0 to Day 30 after each vaccination

A MAAE with missing time of onset will be considered to have occurred just after the vaccination indicated by the visit number, so will be included in the safety analysis tables mentioned above.

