5.1.2 Justification of the Study Design

The MET61 study is part of an ongoing development program that focuses on demonstrating that the safety profile of the MenACYW conjugate vaccine is acceptable and not different from that of licensed quadrivalent meningococcal conjugate vaccines (MCV4), and that the immunogenicity of the MenACYW conjugate vaccine is non-inferior to licensed comparators in direct comparison trials. MET61 is a pivotal Phase III immunogenicity and safety study in which the vaccine candidate will be evaluated in a 1 + 1 schedule in infants/toddlers receiving concomitantly licensed routine pediatric vaccines in the US.

The primary objective of study MET61 is to describe and evaluate the safety and immunogenicity of MenACYW conjugate vaccine compared to the licensed comparator vaccine, MENVEO®, when administered concomitantly with routine pediatric vaccines in US infants and toddlers as a 2-dose series administered at 6 to 7 months of age and 12 to 13 months of age. MET61 will also evaluate the safety and immunogenicity of MenACYW conjugate vaccine and the licensed control vaccine, Menactra®, when administered in US toddlers as a 2-dose series at 17 to 19 months of age and 20 to 23 months of age.

The concomitant administration of standard of care pediatric vaccines together with 5 different administration schedules of the MenACYW conjugate vaccine has been assessed in infants/toddlers 2 to 15 months of age in the US in the MET39 study. The subjects received during, or prior to the study, a number of licensed recommended vaccines at 2, 4, and 6 months of age: Pentacel®, either Prevnar® or Prevnar 13®, RotaTeq® or ROTARIX®, and ENGERIX-B® or RECOMBIVAX HB®. All subjects received M-M-R® II and VARIVAX® at 12 months of age. A total of 457 subjects completed the study. The immunogenicity and safety profiles of selected licensed pediatric vaccines (Pentacel®, Prevnar® or Prevnar 13®, M-M-R® II, and VARIVAX®) were assessed when administered either concomitantly with or without MenACYW conjugate vaccine. There was no evidence of interference with the pediatric routine vaccines administered concomitantly with MenACYW conjugate vaccine and the vaccine was safe and well tolerated regardless of the number of doses administered during the first year of life.

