5.2.7.2 Definitive Contraindications

Prior to vaccination, check the complete list of contraindications for each individual vaccine to be administered. For the licensed vaccines refer to the individual current package inserts. For MenACYW conjugate vaccine refer to the Investigator's Brochure.

Should a subject experience an anaphylactic or other significant allergic reaction to the previous dose of vaccine(s), the Investigator will discontinue vaccination.

The following AEs constitute absolute contraindications to subsequent vaccination with any of the study vaccines. If a subject should experience any of these events during the study, that subject is not to receive any additional study vaccines but should continue in the study and be followed up for safety only as per protocol up to 6 months after the last vaccinations received.

Meningococcal vaccines (MenACYW conjugate vaccine, MENVEO® or Menactra®):

- 1) History of Guillain-Barre syndrome within 6 weeks after vaccination with a tetanus toxoid-containing vaccine.
- 2) History of an Arthus-like hypersensitivity reaction after vaccination with a tetanus toxoid-containing vaccine.
- 3) Severe allergic reaction (e.g., anaphylaxis) after a previous dose of meningococcal capsular polysaccharide-, diphtheria toxoid- or CRM₁₉₇ –containing vaccines or to any component of meningococcal vaccines.

M-M-R®II (measles, mumps, and rubella vaccine):

- 4) Hypersensitivity to any component of the vaccine, including gelatin.
- 5) Anaphylactic or anaphylactoid reactions to neomycin.
- 6) Patients receiving immunosuppressive therapy. This contraindication does not apply to patients who are receiving corticosteroids as replacement therapy, e.g., for Addison's disease.
- 7) Individuals with newly diagnosed (after inclusion in the study) blood dyscrasias, leukemia, lymphomas of any type, or other malignant neoplasms affecting the bone marrow or lymphatic systems.
- 8) Newly diagnosed (after inclusion in the study) primary and acquired immunodeficiency states, including patients who are immunosuppressed in association with acquired immune deficiency syndrome (AIDS) or other clinical manifestations of infection with human immunodeficiency viruses; cellular immune deficiencies; and hypogammaglobulinemic and dysgammaglobulinemic states.

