5.2.11 Follow-up of Discontinuations

The site should complete all scheduled safety follow-ups and contact any subject who has prematurely terminated the study because of an AE, a protocol deviation, or loss of eligibility, including definitive contraindications.

For subjects where the reason for early termination was lost to follow-up or if the subject withdrew informed consent and specified that they do not want to be contacted again and it is documented in the source document, the site will not attempt to obtain further safety information.

If the subject's status at the end of the study is "Withdrawal by Subject or Parent / Guardian / Legally Acceptable Representative", the site will attempt to contact them for the 6-month follow-up except if they specified that they do not want to be contacted again and it is documented in the source document.

For subjects where the reason for early termination is voluntary withdrawal, the site will attempt to contact them for the 6-month follow-up except if they specified that they do not want to be contacted again and it is documented in the source document.

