4.4.4.2 Subject Duration

The duration of a subject in the study is computed as follows: Maximum (date of last visit, date of term form) – (date of Visit 1) +1.

The duration of a subject in the study including follow-up is computed as follows: Maximum (date of last visit, date of term form, last date of follow-up contact) – (date of Visit 1) +1.

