4.4.4.3 Duration of the Study

The duration of the study (until last visit) is computed as follows: Maximum of all subjects (date of last visit, date of termination form) – minimum for all subjects (date of Visit 1) +1.

The duration of the study (including follow-up) is computed as follows: Maximum of all subjects (date of last visit, date of termination form, date of last follow-up contact) – minimum for all subjects (date of visit V01) +1

5 Statistical Methods and Determination of Sample Size

The statistical analyses will be performed under the responsibility of the Sponsor's Biostatistics platform using SAS® Version 9.4 software or later.

For descriptive purposes, the following statistics in [Table 5.1](#) will be presented. The confidence interval (CI) for the single proportion will be calculated using the exact binomial method (Clopper-Pearson method, quoted by Newcombe [\(1\)](#)). For immunogenicity results, assuming that Log₁₀ transformation of the titers / data follows a normal distribution, at first, the mean and the 95% CI will be calculated on Log₁₀ (titers / data) using the usual calculation for normal distribution (using Student's t distribution with n-1 degree of freedom), then antilog transformations will be applied to the results of calculations, in order to provide geometric means (GMs) and their 95% CI.

Table 5.1: Descriptive statistics produced

Baseline characteristics and follow-up description	Categorical data	Number of subjects Percentage of subjects
	Continuous data	Mean, standard deviation, quartiles, minimum, and maximum
Clinical safety results	Categorical data	Solicited: Number and percentage (95% CIs) of subjects Unsolicited: Number and percentage (95% CIs) of subjects, and number of events
Immunogenicity results	Categorical data (seroprotection, vaccine seroresponse, seroconversion, cutoff)	Number and percentage (95% CIs) of subjects
	Continuous data (titer / data)	Log ₁₀ : Mean and standard deviation Anti-Log ₁₀ (work on Log ₁₀ distribution, and anti-Log ₁₀ applied): Geometric mean (GM), 95% CI of the GM Graphical representation by Reverse Cumulative Distribution Curve (RCDC)

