5.2.1.1 Overall Safety Analysis Set for Any Dose

The overall SafAS is defined as those subjects who have received at least one dose of the study vaccines and have any safety data available. All subjects will have their safety analyzed after any dose according to the vaccine received at the first dose.

Safety data recorded for a vaccine received out of the protocol design will be excluded from the analysis (and listed separately).

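### The whole-study MAAE percentage makes no allowance for unequal follow-up, so it runs low if read as a risk; a person-year rate should be reported beside it

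*SAP*

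**What the plan says.** SAP 4.4.2.4 analyses MAAEs over two periods. One is the whole study, "During the entire study period after any dose from D0 to last phone call"; the other is "From Day 0 to Day 30 after each vaccination". SAP Table 4.1 ends the collection window at Day 180 (+30 days) after the last vaccination. The procedures table for Groups 1 and 2 plans 12 months per subject.

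The statistic comes from SAP Table 5.1: "Unsolicited: Number and percentage (95% CIs) of subjects, and number of events". SAP 5.1.3 specifies Clopper-Pearson intervals. Section 4.4.2.4 does not name a denominator. SAP 5.2.1.1 and 5.2.4 point to the overall safety set, meaning subjects who "have received at least one dose of the study vaccines and have any safety data available". That definition sets no minimum follow-up, and SAP 5.3.1 replaces no missing safety data.

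Protocol 5.2.11 describes what happens after discontinuation:

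- For an adverse event, a protocol deviation or loss of eligibility, the scheduled safety follow-up is completed.
- For voluntary withdrawal, the 6-month contact is attempted unless the family has refused contact.
- For children lost to follow-up, or withdrawn with contact refused, "the site will not attempt to obtain further safety information".

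Under Protocol 5.2.7.2, a child who develops a contraindication to further doses is followed "up to 6 months after the last vaccinations received".

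SAP 4.4.4.2 derives a follow-up time for each child ("The duration of a subject in the study including follow-up is computed as follows"), but the SAP text applies it to no safety rate.

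**The concern.** A single percentage with a binomial interval treats every child as observed over the same window. Here that is not so. A lost child with no recorded MAAE adds one to the denominator and nothing to the numerator, however short the observation. A child withdrawn or contraindicated after dose 1 is followed to about six months after that dose and is counted together with children followed for about twelve.

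An MAAE may be common in infants, because unplanned calls and emails to a health care provider count as contacts. Describing safety is the whole of the observational objectives, and the sponsor expects this trial to add to the product's overall safety database. A whole-study percentage that is low by an unstated amount, with an interval that reflects none of it, is harder to carry into that database or to compare with studies whose retention differed.

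**Working it through.** **Figures the plan gives.** The documents state no MAAE risk and no rate of loss from safety follow-up. The nearest figure is in SAP 5.5: 435 enrolled per infant group with at most 40% non-evaluable gives 435 × 0.60 = 261, which reproduces. It concerns the per-protocol immunogenicity set. Infants excluded from that set can still be followed for safety, so 40% is not used as a loss rate.

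**Assumptions.** 12-month window; constant hazard; true 12-month risk p of 50% (MAAE) or 5% (a serious-event scale); a fraction d loses safety contact, unrelated to risk, at times uniform over the window; n = 435 per group.

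**Formulas.**

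- Hazard: λ = −ln(1 − p).
- Risk observed in a child who leaves: r = 1 − (1 − e^(−λ))/λ.
- Crude proportion: (1 − d)·p + d·r.

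**p = 50%.** λ = 0.6931 and r = 1 − 0.5/0.6931 = 0.2787.

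| Loss d | Crude % | Shortfall (points) |
|---|---|---|
| 5% | 48.9 | 1.1 |
| 10% | 47.8 | 2.2 |
| 20% | 45.6 | 4.4 |

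For example, at d = 10%: 0.90 × 0.50 + 0.10 × 0.2787 = 0.478.

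**p = 5%.** λ = 0.0513 and r = 0.0252. The crude figure is 4.88% at d = 5% and 4.50% at d = 20%, a shortfall of 0.1 to 0.5 points.

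**Precision for comparison.** Clopper-Pearson for 218/435 is 45.3% to 54.9%, a half-width of about 4.8 points. For 22/435 it is 3.2% to 7.6%, about 2.2 points.

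**Sensitivity to timing.** If all losses fell at month 1, the 50% risk with 20% loss would give 41.1%, about twice the shortfall.

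**Between groups.** With the same 50% risk in both groups, losses of 10% and 20% give 47.8% and 45.6%, an artificial difference of 2.2 points. At 5% risk it is 0.25 points. With equal risk and equal loss it is zero.

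**Does a person-year rate help?** At p = 50%, a fully followed child contributes 0.50 first events and 0.50/0.6931 = 0.7213 years. A leaver contributes 0.2787 events and 0.2787/0.6931 = 0.4021 years. With d = 20%, events are 0.4557 and time is 0.8 × 0.7213 + 0.2 × 0.4021 = 0.6575, so the rate is 0.4557/0.6575 = 0.693 per year. That equals the rate with no loss. The exact equality depends on the constant hazard.

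**The case against.** The strongest reply is that the SAP claims nothing more than a description. The endpoint is the occurrence of MAAEs during the trial, no hypothesis is tested, and a crude percentage correctly reports how many children had one recorded. That stands. The number is low only when read as a risk over the named window, although a binomial interval invites that reading.

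The plan also limits the problem. The Day 0 to Day 30 MAAE summaries are much less exposed, the per-dose safety sets contain only recipients of that dose, and events before exit are counted. SAP 5.1.4.1 anticipates missed 6-month calls through its COVID-19 subsets, but these are triggered only above 10% impacted and do not account for time observed.

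Several stronger readings are tempting and are not supported:

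- *All infants who leave early go unobserved.* Protocol 5.2.11 keeps most of them in safety follow-up or attempts the 6-month contact. Only those lost or refusing contact are not pursued.
- *Contraindicated infants with dose 1 only have missing follow-up.* Table 4.1 and Protocol 5.2.7.2 end their window six months after the last dose received, so their planned follow-up is complete. They have less time at risk and no dose 2 exposure.
- *About 21% will be lost.* In the Phase II study MET39, 580 were enrolled and "A total of 457 subjects completed the study", so 123/580 = 21% did not complete. That is non-completion in an open-label study of several schedules, not loss of safety contact here.
- *The solicited-reaction analysis already handles this.* SAP 4.4.2.1.2 drops only children with no usable data at all, so it sets no precedent for partial follow-up.
- *The comparison of vaccines is biased.* That needs differential loss, and nothing in this randomised, modified double-blind comparison predicts it.

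**Conclusion.** The concern holds in a limited form, for the whole-study MAAE summary. With no person-time measure and no minimum follow-up, unobserved months count as event-free and shorter times at risk are pooled with longer ones. The crude percentage therefore cannot exceed the full-follow-up risk and falls below it as loss grows. Under the assumptions above the shortfall is about 1.1 to 4.4 points for 5% to 20% loss at a 50% risk, which can approach the interval's half-width without being reflected in it. Risk, loss rate, hazard shape and exit times are all assumed; the documents supply none of them. The denominator is inferred from SAP 5.2.1.1 and 5.2.4.

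A reader might extend this to serious events, but there the shortfall is under about 0.5 points at a 5% risk and needs no separate change. Nothing here touches the immunogenicity objectives. This is an inexpensive improvement to a descriptive safety summary.

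**What to change.** Keep the crude number and percentage. In SAP 4.4.2.4 and Table 5.1, add by group:

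- subjects with a first MAAE per person-year, with an exact Poisson 95% interval;
- total person-time;
- the number reaching the 6-month call.

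Count time from D0 to the first MAAE or the last actual safety contact, whichever is earlier. Do not take the SAP 4.4.4.2 duration unchanged: it uses the latest of several dates, including the termination form, and could credit a lost child with time nobody observed. MAAEs with missing onset can follow the existing convention in 4.4.2.4.

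Do not use a Kaplan-Meier estimate to Day 180 after dose 2. That time point does not exist for a child without dose 2. It is also not a common time from D0, because Visit 3 falls at six months or more after Visit 1.

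Separately, reconcile the final call, which sets the end of the window. The procedures table for Groups 1 and 2 places it at Visit 3 + 180 days, while Protocol 5.1.4.1 places it 180 [+30] days after Visit 4. Visit 4 is itself 30 (+21) days after Visit 3, so the two target dates differ by 30 to 51 days. Protocol 5.1.4.2 also times the call from Visit 4 for Groups 3 and 4, which have only three visits.

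The cost is SAP wording and a few table entries from dates the trial should already hold, with no new data or subjects. The small downside is one more statistic alongside the crude percentages.

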4.3.1.3.5 Medically-Attended Adverse Events

MAAE information will be collected throughout the study. MAAEs will be recorded as unsolicited AEs for up to D30 after each vaccination and as MAAEs until the next study visit on the appropriate diary cards. MAAEs that occur from D31 after the last vaccination visit until the 6-month follow up phone call will be recorded as such in the appropriate memory aid. An MAAE that occurs within the study period but meets the definition of an SAE should be reported only on the SAE Reporting Form. The Investigator will assess the causal relationship between the MAAE and the investigational or study product as “Not related” or “Related”.

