5.3.1.4 Start Date and Stop Date

Missing or partially missing start dates or end dates for unsolicited AEs (including SAEs) will remain missing and not be imputed. If the start date is missing or partially missing, the time of onset will be considered to be missing. Nevertheless, unsolicited AEs with missing time of onset will be included in analyses within or not within the defined time window (according to the [section 4.4.2.2.4](#)), according to the last vaccination (computed according to the [section 4.4.2.2.3](#)). If either the start date or end date is missing or partially missing, the duration will be considered missing.

Missing or partially missing end dates for ongoing solicited AEs will remain missing and not be imputed.

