5.7 Changes in the Conduct of the Trial or Planned Analyses

For MET61 study, concomitant medications category fields were inactivated, and concomitant medications were coded with WHODrug dictionary by the coding specialists.

Two additional population analysis sets for persistence immunogenicity analysis after infant vaccination (FAS3 and PPAS3) and the corresponding definitions were added as those populations of analysis were not pre-defined in the protocol.

Sections 4.4.2.2.3, 4.4.2.2.4 and 5.3.1.4 were updated according to new version of the Standard Safety Tables.

6 References List

- 1 Newcombe R.G., Two-sided confidence intervals for the single proportion: comparison of seven methods, *Statistics in Medicine*, (1998) 17, 857-872
- 2 Newcombe RG. Interval Estimation for the difference between independent proportions: comparison of eleven methods. *Stat Med*. 1998; 17(8):873-90

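### SAP 4.4.2.4 puts every MAAE with a partial start date in the Day 0-30 table, against the SAP's own partial-date rule in 4.4.2.2.4

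*SAP*

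**What the plan says.** SAP 4.4.2.4 plans two MAAE periods: the whole study, and Day 0 to Day 30 after each vaccination. For missing onset it states: "A MAAE with missing time of onset will be considered to have occurred just after the vaccination indicated by the visit number". It adds that these events are therefore counted in the tables for those periods.

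Two sections define missing onset. SAP 4.4.2.2.4: "The time of onset is considered as missing only if one or both dates are missing or partially missing". SAP 5.3.1.4: "If the start date is missing or partially missing, the time of onset will be considered to be missing". A start date with a known month and year but no day therefore has missing onset.

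For unsolicited AEs, SAP 4.4.2.2.4 then uses whatever part of the date is known. The event is outside 30 days only when the known month or year clearly places it before the first vaccination or later than 30 days after the last. SAP 5.3.1.4 refers to that rule and accepts that an event with missing onset may be in or out of the window.

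The same section has a closing note that recommends this rule but makes it "possible to follow the below rule, for homogeneity need". The alternative is: "An AE with missing time of onset will be considered to have occurred just after the last vaccination".

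SAP 5.7 reports: "Sections 4.4.2.2.3, 4.4.2.2.4 and 5.3.1.4 were updated according to new version of the Standard Safety Tables". Section 4.4.2.4 is not in that list.

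**The concern.** Read with the definition of missing onset, the 4.4.2.4 sentence overrides date information that the SAP uses elsewhere. An MAAE known only to have begun in the fifth month after the dose would be counted in the Day 0-30 table.

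SAP 4.4.2.2.4 is not silent on MAAEs. For events classified as outside 30 days it says: "If the AE is non-serious, non-AESI and non-MAAE, then it will not be included in the analysis but will be listed separately". That exemption is needed only if some MAAEs can be outside 30 days. SAP 4.3.1.3.5 adds that "MAAEs will be recorded as unsolicited AEs for up to D30 after each vaccination", so the two kinds of table draw on overlapping records. One event could be outside 30 days in one table and inside it in the other.

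MAAEs are a stated safety endpoint (Protocol 9.3.2.2; SAP Table 4.1), and Day 0-30 is one of only two planned periods. Adding late events to the early window misstates their timing in every group and could blur a difference between vaccines as easily as show one. The whole-study table is affected only by events dated before vaccination: 4.4.2.2.4 sends these to a listing with no MAAE exemption, while 4.4.2.4 read literally counts them.

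**Working it through.** **Rules applied.**
- Rule A (4.4.2.2.4): a fully missing date is within 30 days. Otherwise compare the known month and year (or year alone) with the first vaccination and with the last vaccination + 30 days. Earlier than the first: not analysed. Later than the second: not within 30 days. Anything else: within.
- Rule B (4.4.2.4): missing onset is placed just after vaccination, so it is always in Day 0-30.

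The rules agree on which dose the event follows: for partial dates 4.4.2.2.3 also uses the visit number. They differ on the window.

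**The SAP's nine worked examples.** Rule A reproduces all nine stated answers.

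| Injection | AE start | Injection + 30 days | SAP answer | Rule A | Rule B |
|---|---|---|---|---|---|
| 16Oct2023 | missing | n/a | Y | Y | Y |
| 16Oct2023 | Sep2023 | n/a | N | N (before dose) | **Y** |
| 16Oct2023 | Oct2023 | 15Nov2023 | Y | Y | Y |
| 16Oct2023 | Nov2023 | 15Nov2023 | Y | Y | Y |
| 16Oct2023 | Dec2023 | 15Nov2023 | N | N (after Day 30) | **Y** |
| 05Jan2023 | 2022 | n/a | N | N (before dose) | **Y** |
| 16Oct2023 | 2023 | 15Nov2023 | Y | Y | Y |
| 08Dec2023 | 2024 | 07Jan2024 | Y | Y | Y |
| 16Oct2023 | 2024 | 15Nov2023 | N | N (after Day 30) | **Y** |

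Rule A gives 5 Y and 4 N; Rule B gives 9 Y. They disagree on 4 of 9, or 4 of the 8 partial dates, since the first row is fully missing. Two disagreements are after Day 30 and two are before the dose.

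**Follow-up time exposed after the last dose.** MAAEs are collected to Day 180 (+30 days). With month and year known, the rules disagree in every calendar month after the month containing Day 30.

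Share = (days after the end of that month, up to the last day of follow-up) / (days from Day 0 to the last day of follow-up).

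For the 16Oct2023 example, Day 30 is 15Nov2023, so disagreement starts on 1 December:
- To Day 180 (13Apr2024): 31 + 31 + 29 + 31 + 13 = 135 days; 135/181 = 74.6%, 5 of 7 calendar months.
- To Day 210 (13May2024): 135 + 17 + 13 = 165 days; 165/211 = 78.2%, 6 of 8 calendar months.

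Over every possible vaccination date in 2019-2022:
- To Day 180: 66.3% (120/181) to 82.9% (150/181), mean 74.7%.
- To Day 210: 71.1% (150/211) to 85.3% (180/211), mean 78.3%.

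If only the year is known, the same calculation uses the year boundary and the share to Day 180 runs from 0% to 83%. It is zero when Day 180 falls in the same calendar year as Day 30.

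**The case against.** The strongest defence is that 4.4.2.4 is a rule specific to one endpoint, that the note in 4.4.2.2.4 allows the same method, and that it errs towards inclusion equally in all groups. On that view the SAP need only say which option applies to MAAEs. This does not remove the conflict. The SAP recommends the main rule, nowhere says that this trial adopted the alternative, and follows the main rule in 5.3.1.4. The MAAE exemption in 4.4.2.2.4 also assumes that some MAAEs are outside 30 days.

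Some narrower points stand:
- The pre-dose examples should seldom arise, because MAAE collection starts at Visit 1 and the whole-study period starts at Day 0. The practical conflict is mainly the events after Day 30.
- The overlap between the tables rests more on the MAAE exemption than on 4.3.1.3.5, which describes recording only up to Day 30.
- The worked examples are illustrations, not a sample of events, and 16Oct2023 is later than the planned end of study, 25 August 2023 (Protocol 5.1.5).
- The 66% to 83% range assumes that month and year are known.
- If the last vaccination in 4.4.2.2.4 means the final dose, partial dates between doses are within 30 days under both rules.
- Start dates are a required item and queries must be closed before database lock, so the affected records may be few.

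**Conclusion.** The concern holds. Given the SAP's own definition of missing onset, the sentence in 4.4.2.4 puts MAAEs known to be late, and literally also those known to precede vaccination, into the Day 0-30 table. It contradicts 4.4.2.2.4 on 4 of the SAP's 9 worked examples. This is a stated rule that gives a wrong classification, not a missing detail.

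The change in any reported MAAE percentage cannot be computed and may be small. The exposed share, 66% to 83% of days to Day 180 and 71% to 85% to Day 210, is a share of follow-up time after the last dose with month and year known. It is not a share of MAAEs. Only descriptive safety tables are affected; the primary and secondary hypothesis tests are not.

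The omission of 4.4.2.4 from the list in 5.7, and its likeness to the optional alternative, suggest that it was overlooked when the other sections were updated. That is an inference.

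**What to change.** 1. In SAP 4.4.2.4, replace the missing-onset sentence with: MAAEs with missing or partial start dates are classified by the partial-date rule of 4.4.2.2.4.
2. In 4.4.2.2.4, delete the optional alternative in the closing note, so that one rule governs unsolicited AEs and MAAEs.
3. Add 4.4.2.4 to the updated sections listed in 5.7.

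Stating that the alternative applies to all unsolicited AEs, MAAEs included, would also make the tables agree. It would, however, discard known months and years, and 5.3.1.4 and the worked examples would have to change with it.

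The cost is SAP wording and minor programming. No new data are needed, because the partial date is already used under 4.4.2.2.4.
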